Bioactive glass (S53P4) is an established synthetic biocompatible bone graft substitute which stimulates bone formation and improves blood supply in the affected areas. Furthermore, bioactive glass is established in the therapy of bone inflammation. The therapy of large bone defects consists of a two- or multi-stage procedure and is called Masquelet therapy. In a first procedure the bone is locally conditioned and in a second procedure the bone defect is filled with a combination of autologous bone and tricalcium phosphate. This autologous bone is obtained from RIA (Reaming-Irrigating- and Aspirating) material of the ipsi- or contralateral femur or from iliac crest cancellous bone with tricalcium phosphate. However, this requires another surgical procedure to obtain the bone graft, which is associated with risks and may cause additional problems for the patient. Multiple studies have shown that filling bone defects with bioactive glass leads to new bone formation and bone regeneration. This could lead to the elimination of the need for autologous bone grafting, thus avoiding the need for further surgical intervention. The planned clinical study will compare the effects on osseous consolidation of pseudarthrosis at the tibia and femur between standard Masquelet therapy (G1) and Masquelet therapy using bioactive glass as bone graft substitute (G2). The study will include 50 patients with pseudarthrosis of the femur and tibia in a prospective randomized design. After randomization, 25 patients will be treated with either Masquelet therapy (G1) or Masquelet therapy using bioactive glass as replacement material (G2).

The clinical course will be evaluated preoperatively, 2 days, 6 and 12 weeks and 6,9, 12 and 24 months postoperatively. In addition to clinical and nativradiological standard control examinations, perfusion is examined by CEUS ultrasound (contrast enhanced ultrasound) and dynamic contrast enhanced MRI (DCE -MRI) preoperatively and 12 weeks postoperatively. Furthermore, blood samples are taken to check the infection levels, local blood flow situation and bone growth markers.

2) Introduction / Scientific Basis:

Bone has the ability to regenerate after injury in a complex physiological process. However, this process can be disturbed in extensive injuries and critical blood supply or infectious situations and delayed fracture healing is a serious complication in trauma surgery (1). Depending on the individual patient risk, 5-10% of all fractures lead to pseudarthrosis. The tibia is most frequently affected (2). Pseudarthrosis is not only a common complication but also leads to serious consequences. Pain, immobilization, and loss of the affected limb pose significant limitations for patients (3). The complex pathophysiology of delayed or failed fracture healing requires multifactorial treatment. The so-called Diamond concept (4) consists of the following components:

- Biomechanical stability: angular stable plates, dynamic intramedullary nails.
- Osteogenic cells: mesenchymal stem cells, autologous cancellous bone (iliac crest or RIA)

- Osteoconductive structures: autologous cancellous bone, synthetic bone substitutes
- Growth hormones: bone morphogenic proteins (BMP-2 and BMP-7)
- Circulation: by improving macro- and micro-circulation, local induction of a Masquelet membrane and debridement of fracture ends.

Although autologous bone grafting is the gold standard for filling bone defects, it is associated with great morbidity for the patient and availability is limited (2). Therefore, in the last decades, there has been an intensive search for suitable bone graft substitutes that could lead to new bone formation and reduce the need for autogenous bone grafting in the future. Initial studies have shown that bioactive glasses have an outstanding antibacterial effect, which can be attributed to an increase in local PH and osmotic pressure (5). Surprisingly, during follow-up of these initial studies, scientists found extensive new bone formation in patients treated with bioactive glass. This led to intensive research efforts to investigate bioactive glass as a bone graft substitute. It was found that bioactive glass with the composition of SiO₂, Na₂O, CaO and P₂O₅ initiates growth of tissue and stimulates bone growth (5-9). The effect of bioactive glass is based on the release of ions (Si⁺, Na⁺, Ca²⁺) and their reaction with body fluids. After application in situ, these surface reactions lead to the formation of a calcium phosphate layer that bonds with solid materials such as bone (10). Numerous studies have demonstrated the clinical efficacy of this mechanism in oral and maxillofacial surgery (11, 12), spine surgery (13), and trauma surgery (5, 7-9, 13). Furthermore, numerous studies demonstrated the safety of the clinical application of bioactive glass for filling bone defects (5, 7-9, 13). However, there are no clinical studies evaluating the use of bioactive glass in masquelet therapy of pseudarthrosis. Contrast-enhanced ultrasound (CEUS) as well as dynamic contrast-enhanced magnetic resonance imaging can visualize the vascularization of pseudarthrosis in real time. In this regard, CEUS and DCE-MRI can be used preoperatively to differentiate between infectious and noninfectious pseudarthroses (14, 15). Postoperatively, DCE- MRI provides a valid tool for predicting bony consolidation of pseudarthrosis (16). Perioperative cytokine measurement of bone growth markers is a well-established method that provides an early indication of whether local infection is present or healing is likely (17, 18).

Bioactive glass (S53P4) is approved for the treatment of bone defects in pseudarthrosis in Germany.

Literature:

1. Einhorn TA. The cell and molecular biology of fracture healing. Clin Orthop Relat Res. 1998(355 Suppl):S7-21.

4.1 General description

The current study will compare two groups of patients. One group will receive standard therapy for pseudarthrosis of the femur or tibia in terms of two-stage or multi-stage Masquelet therapy. In the second group, transplantation of autologous cancellous bone is omitted in the second stage of Masquelet therapy and bioactive glass is used instead. Clinical follow-up of pseudarthrosis patients is standardized in our department and no additional examinations are performed as part of the study. As an extension of the clinical follow-up examinations, only blood samples will be taken as part of the study to determine growth factors, infection parameters, and blood flow markers. The total collection volume of 32 ml of whole blood per follow-up is small.

4.2 Effects

Bioactive glass with the composition of SiO₂, Na₂O, CaO and P₂O₅ initiates growth of tissues, stimulating bone growth (5-9). The effect of bioactive glass is based on the release of ions (Si⁺, Na⁺, Ca²⁺) and their reaction with body fluids. After application in situ, these surface reactions lead to the formation of a calcium phosphate layer that bonds with solid materials such as bone (10). Numerous studies have demonstrated the clinical efficacy of this mechanism in oral and maxillofacial surgery (11, 12), spine surgery (13), and trauma surgery (5, 7-9, 13). Furthermore, numerous studies demonstrated the safety of the clinical use of bioactive glass for filling bone defects (5, 7-9, 13). If these results are confirmed in the current study, this represents a promising possibility for avoiding the additional intervention required to obtain the bone graft in the future.

4.3 Adverse effects/risks

Bioactive glass (S53P4) is approved for the treatment of bone defects in pseudarthrosis in Germany. Risks are assumed to be the usual surgical risks, but the indication for surgical therapy will be based on purely medical reasons and will be completely independent of the study. Furthermore, the patient may not respond to the therapy, which may result in

persistent pseudarthrosis. However, this risk exists for both standard therapy and Masquelet therapy with bioactive glass as bone substitute. Follow-up examinations are performed according to the same standard that is used for all patients treated in our clinic. Thus, there is no undesirable burden on the patient. Only blood samples are taken in addition to the standard. Possible undesirable effects of this blood collection correspond to the blood collection that is normally performed in the clinic or by the general practitioner. The amount of blood drawn includes 4 tubes, which is equivalent to 32 ml of blood. This has no relevant influence on the total amount of blood. However, possible undesirable side effects may still occur:

Pain at the puncture site, secondary bleeding, hematoma ("bruise"), infection (very rare), vagal reaction with hypotension, nausea and possibly syncope ("fainting"), dizziness and feeling of weakness after blood collection.

5) Study design

Investigator initiated Study

Clinical post-marketing observation study

Prospective randomized pilot clinical trial (RCT)

6) Randomization procedure

Balanced randomization, patients will be alternately assigned to treatment group G1 and G2 according to randomization time point.

7) Inclusion criteria

Patients suffering from pseudarthrosis of the tibia or femur with large bone defect (2-5cm³) and operated by Masquelet technique.

8) Exclusion criteria

Patients under 18 years of age

Patients who do not consent to participate in the study.

Patients who require amputation of the affected limb due to persistent infections or extensive soft tissue defects.

9) Discontinuation criteria

General: preliminary data or external data indicate unexpected risks to patients.

Individual: patients wish to discontinue their participation in the study

10) Study procedure

Patients suffering from pseudarthrosis with a large bone defect (2-5 cm³) will be treated with the standard masquelet technique.

After written and verbal information to the patients, a total of 50 patients will be randomized. All patients will receive a CEUS ultrasound examination and a DCE MRI examination preoperatively to evaluate local perfusion.

Subsequently, in the first step of the Masquelet technique, inset implants are removed, the pseudarthrosis is debrided, and a PMMA cement spacer is inserted after reduction. Either internal or external fixation is performed depending on stability and soft tissue conditions. During the first procedure, tissue samples are taken for microbiological examination. If germs are positive, this procedure is repeated until all microbiological samples are germ-free. Step two of the Masquelet technique is then performed six weeks postoperatively. The PMMA cement is completely removed and the bone defect is filled with a combination of autologous bone and a tricalcium phosphate matrix (G1) or bioactive glass (G2).

Subsequently, all patients receive the same standardized follow-up examinations. Initial clinical and native-radiologic follow-up examinations are documented two days postoperatively, and patients are discharged to outpatient care as soon as soft tissue conditions permit. All patients also receive physical therapy in the outpatient setting. Clinical and radiological follow-up examinations in our outpatient clinic are performed 6 weeks, 3 months, 6 months, 12 months, and 24 months postoperatively (see Table 1). Signs of infection, range of motion of adjacent joints, pain (Visual Analog Scale), and weight-bearing are obtained during the clinical examination. All radiological data are collected as part of the clinical necessity; no additional radiological examinations are performed.

A questionnaire is used to document preoperative and 3,12 and 24 months postoperative information on pain and range of motion, ability to work and quality of life.

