12.2.3 Data destruction in case of withdrawal

In the event of withdrawal from the study, all data not already published will be destroyed, unless the patient has given prior written consent for the data already collected to be evaluated.

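### Allocation precedes a common first stage of at least six weeks, is foreseeable through alternation, and by default leaves no record of patients who withdraw in between

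*Protocol*

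**What the plan says.** Section 10 (Study procedure) opens the trial sequence with "After written and verbal information to the patients, a total of 50 patients will be randomized". Preoperative CEUS and DCE-MRI come next, then step one: implant removal, debridement and a cement spacer, described once for all patients. If cultures are positive, "this procedure is repeated until all microbiological samples are germ-free. Step two of the Masquelet technique is then performed six weeks postoperatively". No limit is given on the number of repeats.

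Section 4.1 says where the arms part: in the second group, "transplantation of autologous cancellous bone is omitted in the second stage of Masquelet therapy and bioactive glass is used instead". Section 10 agrees; the filling at step two is the only difference it describes.

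Section 6 (Randomization procedure) sets the method: "patients will be alternately assigned to treatment group G1 and G2 according to randomization time point". Section 9 gives one individual ground for discontinuation: "Individual: patients wish to discontinue their participation in the study".

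Section 12.2.3 governs the data afterwards: "In the event of withdrawal from the study, all data not already published will be destroyed". It makes a single exception, in that the rule applies "unless the patient has given prior written consent for the data already collected to be evaluated".

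**The concern.** For at least six weeks, and longer if step one is repeated, patients have an allocation but no difference in treatment. This interval adds nothing to the comparison of fillings, yet any loss during it is a loss after randomisation.

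Early randomisation alone does no harm to validity if every patient is kept and analysed. Two other rules make it matter here. Under alternation, each allocation after the first can be read from the one before it, so whoever enrols can foresee the next patient's arm. And unless prior written consent was given, a patient who withdraws leaves no unpublished data, so that patient cannot even be counted or imputed in the assigned arm. If those lost differ between the arms in prognosis, the remaining groups are no longer the ones that allocation produced.

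**Working it through.** **Order of events, from the text.** Information, randomisation, preoperative imaging, step one (repeated if needed), six weeks, step two. Allocation precedes step one; the arms diverge at step two.

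**The plan's own figure.** Alternating 50 patients gives 25 and 25, which matches the summary. The protocol gives no consolidation rate, loss rate or power, so all rates below are assumptions.

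**Test.** Section 11 names a Wilcoxon test at 0.05 for categorical endpoints. I read it as the tie-corrected rank-sum test, two-sided, without continuity correction. For x1 of n1 against x2 of n2 consolidated, with N = n1 + n2 and pooled proportion p:

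z² = [(N − 1)/N] × (x1/n1 − x2/n2)² / [p(1 − p)(1/n1 + 1/n2)]

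Rejection probabilities are exact sums over the two binomial distributions.

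**False positives.** True consolidation is 60% in both arms, with 25 allocated to each. A fraction f of an arm is lost and its data removed; the lost patients would have consolidated at rate q. The rate among those analysed is (0.60 − f·q)/(1 − f), and the number analysed is binomial(25, 1 − f). For example, f = 0.2 and q = 0.3 gives (0.60 − 0.06)/0.80 = 0.675, and f = 0.2 and q = 0 gives 0.60/0.80 = 0.75.

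| Loss, arm A / arm B | q | Apparent rates | False-positive rate |
|---|---|---|---|
| none / none | – | 60% / 60% | 6.0% |
| 10% / none | 0.6 | 60% / 60% | 5.3% |
| 10% / none | 0.3 | 63.3% / 60% | 5.8% |
| 10% / none | 0 | 66.7% / 60% | 7.7% |
| 20% / none | 0.6 | 60% / 60% | 5.1% |
| 20% / none | 0.3 | 67.5% / 60% | 7.9% |
| 20% / none | 0 | 75% / 60% | 18.1% |
| 20% / 10% | 0.3 | 67.5% / 63.3% | 5.8% |
| 20% / 10% | 0 | 75% / 66.7% | 8.8% |

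The reference value is 6.0%, not 5%, because the test is slightly liberal with 25 per arm. The 5.8% entries therefore show no inflation over the no-loss case. Loss unrelated to outcome (q = 0.6) causes none either.

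**Power.** Under early randomisation with lost patients counted as not consolidated, both rates are multiplied by (1 − f). Under late randomisation, 50 consents yield 50 × 0.9 = 45 patients (22 and 23) or 50 × 0.8 = 40 patients (20 and 20).

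| True rates | No loss | Early, 10% | Late, 10% | Early, 20% | Late, 20% |
|---|---|---|---|---|---|
| 80% vs 50% | 63.8% | 53.6% | 55.2–58.1% | 44.7% | 53.1% |
| 80% vs 60% | 35.2% | 28.2% | 30.4–31.0% | 23.8% | 29.1% |

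The range at 10% depends on which arm has 22 patients. The gain exists only if lost patients count as failures. If equal losses unrelated to outcome were left out, early and late randomisation would have the same power.

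**The case against.** **No motive for unequal withdrawal is shown.** A reader might infer one from the summary, which says of autologous grafting that "this requires another surgical procedure to obtain the bone graft, which is associated with risks and may cause additional problems for the patient", a burden that falls on G1 only. The documents do not support that step. G1 is the standard therapy, and Section 4.3 makes the surgical indication independent of the study. A G1 patient who leaves would by default still have the graft harvest, and nothing says that glass is offered outside the trial. This objection stands: arm-dependent loss is possible but not established.

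**Destruction does not cause the missing outcome.** A patient who withdraws before step two has no one-year radiograph for the trial, whether or not earlier data are kept, and the handling of missing outcomes may be in an analysis plan that is not shown. This stands in part. No analysis plan can count or impute a patient whose record is gone, so the default rule closes an option that the plan would otherwise have. Section 12.2.3 already contains the consent exception, and whether the consent form uses it cannot be seen.

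**Alternation does not reveal the arm during step one.** Once allocation is disclosed, the arm is known under any method. That is correct. The harm particular to alternation is foreseeability at enrolment, and moving the time point alone would not cure it.

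**The time point is inferred.** No sentence fixes it; Section 6 refers only to a randomisation time point, and the inclusion criterion speaks loosely of patients operated on by the technique. But the order in Section 10 is plain, and if step two is meant, the same edit resolves the matter.

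**Amputation.** The criterion in Section 8 might be read as removing randomised patients between the steps. It is written as an entry criterion and carries no weight here.

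**Conclusion.** The point holds in limited form. As Section 10 is ordered, allocation comes at least six weeks before the arms differ, by a method that makes the next allocation foreseeable, and the default data rule leaves nothing to analyse for those who withdraw in between.

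Bias follows only if loss depends on both arm and prognosis. Under the assumed 60% consolidation, the false-positive rate then ranges from no inflation (5.8% against 6.0% without loss) to 8.8% when 20% of one arm and 10% of the other are lost. The 18.1% figure should not be taken as the expected size: it needs 20% loss in one arm, none in the other, and every lost patient a would-be failure.

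Power is a secondary argument. The gain is about 2 to 8 points across the cases shown and rests on counting lost patients as failures. The main benefit of change is that losses before step two would occur before allocation and could not differ by arm because of it. That is worth having in a pilot trial of 50 at this cost, although the present plan is not shown to be biased.

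**What to change.** Keep consent and baseline tests where they are. In Section 10, state that randomisation takes place directly before step two, once the protocol's own germ-free condition is met. In Section 6, replace alternation with a concealed, computer-generated random sequence. At enrolment, ask for the written consent that Section 12.2.3 already allows, so that data collected before a withdrawal can be used. This preserves baseline and step-one data; it does not supply a missing outcome, and the later time point does not affect withdrawals after step two.

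The cost is wording in Sections 6 and 10 and the consent form, plus an allocation list; no visit or procedure is added. Planning for step two must allow for either arm. At 10% or 20% loss between the steps, about 45 or 40 patients are randomised from 50 consents. Keeping 50 randomised would need 50/0.9 = 55.6, so 56, or 50/0.8 = 62.5, so 63 consents within the two-year inclusion period.

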12.1 Ethical principles

The study will be conducted in accordance with the Declaration of Helsinki as amended in October 2013.

12.1.1 Patient/subject information/consent form

Patients will be informed about the study in advance, both verbally and in writing. Participation is voluntary and patients will provide written informed consent.

12.2 Legal basis

The study will be conducted in accordance with the Declaration of Helsinki and the Professional Code of Conduct for Physicians of the State Medical Association of Baden-Württemberg in the respective current versions.

All X-ray examinations performed will be performed as part of routine clinical follow-up examinations. No additional radiographs will be performed as part of the study.

12.2.1 Vote of the Ethics Committee

The study plan will be submitted to the Ethics Committee of the Heidelberg Medical Faculty for review prior to study initiation. The inclusion of subjects/patients will not be started until the written vote of the Ethics Committee has been received.

12.2.2 Data protection/view of original medical records

The names of patients and all other confidential information are subject to medical confidentiality and the provisions of the German Federal Data Protection Act (BDSG). Patient data may only be passed on in anonymized form. Third parties will not be given access to original medical records.

12.2.3 Data destruction in case of withdrawal

In the event of withdrawal from the study, all data not already published will be destroyed, unless the patient has given prior written consent for the data already collected to be evaluated.
